#### 7.2.8. Cutaneous Lupus Erythematosus Area and Severity Index (CLASI)

The CLASI is a comprehensive tool for assessment of disease activity and damage in cutaneous lupus, shown to be valid, reliable, and sensitive to changes in disease activity.

The total activity score will be calculated by summing the scores on the left side of the form (erythema, scale/hypertrophy, mucous membrane, alopecia – recent hair loss and alopecia clinically not obviously scarred).

The total damage score will be calculated by:

- (1) Sum the responses for “Dyspigmentation” in all anatomical locations
- (2) If a response for “Report duration of dyspigmentation after active lesions have resolved” is “Dyspigmentation usually lasts at least 12 months”, then multiply the sum in #1 by 2.
- (3) If a response for “Report duration of dyspigmentation after active lesions have resolved” is “Dyspigmentation usually lasts less than 12 months”, then the sum in #1 will not change.
- (4) If the sum in #1 is 0 and a response for “Report duration of dyspigmentation after active lesions have resolved” is missing, then the sum in #1 will not change.
- (5) Determine the Dyspigmentation Score based on the results from 2, 3, or 4.
- (6) Sum the remaining scores on the right side of the form (scarring/atrophy/panniculitis, alopecia - scarring of the scalp judged clinically).
- (7) Sum the scores from #5 and #6 to obtain the total damage score.

If any individual scores which contribute to the total activity score or the total damage score are missing, the total score in question will not be calculated. If total activity score or total damage

Sponsor: Boston Pharmaceuticals, Inc.  
Protocol Number: BOS161721-02  
SAP Version and Date: Version 4.0, 23Apr2021

score are missing at a visit, LOCF methods will be implemented as described in Section [5.4](#) and Section 7.2.1 for the “at each visit” analyses.

The mean and SD of the change from baseline in CLASI total activity and total damage scores will be presented graphically over time by study phase and treatment group.

#### 7.2.8.1. Proportion of Patients with CLASI Response

CLASI response is defined as 50% improvement from baseline in CLASI. A CLASI-A response applies to “A” (total activity) and a CLASI-B response applies to “B” (total damage) score.

Statistical methods described in Section 7.1.1 will be implemented. In case of missing data, LOCF methods will be implemented as described in Section 5.4 and 7.2.1 for the “at each visit” analysis. Individual components of the CLASI will not be carried forward; however, the total activity score or total damage score may be carried forward from the most recent prior visit. If the most recent prior visit is missing, occurred more than 30 days before (current visit date – most recent prior visit date > 30), or is not evaluable, LOCF is not implemented. The primary analysis methods (LOCF for missing data, medication failure=non-responder) as described in Section 7.1.1 and Table 2 will be performed at each visit based on the CLASI response definition and will be presented by study phase and treatment group in the FAS.

CCI

The analysis will also be repeated in line with Sensitivity Analysis 2 (LOCF for missing data, exclude medication failures) in Section 7.1.1.

Other analyses described in Section 7.1.1 may also be performed.

The denominators for analyses will be the number of patients in the FAS with an evaluable post-baseline CLASI assessment (whether observed or imputed via LOCF depending on the analysis) at a given visit.

Statistical testing data will be omitted from MAD Phase 1b treatment group displays.

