## 5.4. Baseline, Post-Baseline Changes, and LOCF

Unless stated otherwise, baseline and post-baseline change values will be based on the following:

- Baseline will be based on the last non-missing value collected prior to or on the date/time of first dose of study drug.
- Post-baseline values will be those collected after the date/time of first dose of study drug.
- Change from baseline is defined as: value – baseline value.
- Percentage change from baseline is defined as:  $[(\text{value} - \text{baseline value}) / \text{baseline value}] * 100$ . Patients with baseline values of zero are excluded due to division by zero.
- Most extreme change: The maximum most extreme change will be the maximum post-baseline change value; the minimum most extreme change will be the smallest post-baseline change value. This calculation will consider all assessments collected after the first dose of study drug, scheduled or unscheduled.
- LOCF:
  - Imputation rules for assessments that include multiple components:
    - In case of missing laboratory components, lab values from the most recent unscheduled visit  $\leq 14$  days after the nominal visit will be utilized. If lab values are not available from an unscheduled visit  $\leq 14$  days after the visit, laboratory data will be carried forward from the most recent laboratory assessment  $\leq 30$  (scheduled or unscheduled) days prior to the nominal visit.
    - In case of missing non-laboratory components, no imputation will be performed.
  - In case of missing the entire score for an assessment, imputation will be based on LOCF. LOCF will only be implemented with the most recent prior visit (including unscheduled assessments). If the most recent prior visit is missing, occurred more than 30 days before (current visit date – most recent prior visit date  $> 30$ ), or is not evaluable, LOCF is not implemented. See Section 7 for further details. Additional details regarding LOCF for components for specific assessments are described in Section 7.
  - Observed values do not incorporate any imputations and are presented as collected.

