#### **Missing Data:**

- **Pre-Treatment:** If a patient is missing data during the pre-treatment period for SLEDAI-2K, PGA, or BILAG, the patient will be excluded from the primary efficacy analysis.

- **Overall SRI-4 Components:** Missing data at Day 210 for overall components for SLEDAI-2K, BILAG, and PGA will be addressed by employing a LOCF analysis within each overall component as described in Section 5.4. For example, if a patient has data for SLEDAI-2K and BILAG at Day 210 but is missing PGA at Day 210, the PGA component would employ LOCF as described in Section 5.4. If the overall component is missing from Day 180 through Day 210 and the patient is not a medication failure on or prior to Day 210 and did not withdraw/discontinue treatment prior to Day 180, the SRI-4 response at Day 210 will be considered not evaluable.
- **Individual Items Contributing to Overall SRI-4 Components:** Data collection and scoring will be performed in the clinical database for BILAG, SLEDAI-2K, and PGA. If missing individual items contributing to any of the overall components occurs for Day 210, the overall component will be recalculated per the Table 1.

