#### Mucous membrane

#### Dyspigmentation

|   |   |
|---|---|
| Mucous membrane lesions (examine if patient confirms involvement) | Report duration of dyspigmentation after active lesions have resolved (verbal report by patient – tick appropriate box) |
| 0-absent;
1-lesion or ulceration                               |  Dyspigmentation usually lasts less than 12 months (dyspigmentation score above remains)        |
|   |  Dyspigmentation usually lasts at least 12 months (dyspigmentation score is doubled)            |

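### CLASI response sets no baseline-above-zero condition on its denominator, and CLASI-B can fall by up to 50% on a changed duration answer alone

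*SAP*

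**What the plan says.** Section 7.2.8.1 states: "CLASI response is defined as 50% improvement from baseline in CLASI". It applies this separately to total activity (CLASI-A) and total damage (CLASI-B), at each visit, with the test methods of Section 7.1.1 and the primary-analysis handling of medication failures and early withdrawals as non-responders. On who is counted it says: "The denominators for analyses will be the number of patients in the FAS with an evaluable post-baseline CLASI assessment", whether observed or carried forward. Nothing is said about the baseline score.

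Section 5.4 has a general rule for percentage change: "Patients with baseline values of zero are excluded due to division by zero". That rule is a default, introduced by "Unless stated otherwise, baseline and post-baseline change values will be based on the following".

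Section 7.2.8 builds the damage score. The dyspigmentation items are summed over the anatomical sites. If the patient reports that dyspigmentation usually lasts at least 12 months, "then multiply the sum in #1 by 2"; if less than 12 months, "then the sum in #1 will not change". The scarring and scalp items are then added without doubling. The form in Appendix 13.7 carries the same instruction, "Dyspigmentation usually lasts at least 12 months (dyspigmentation score is doubled)", and records the answer as a verbal report by the patient. The form has a visit field, and no section fixes the answer at its baseline value.

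**The concern.** CLASI response is a Phase 2 secondary endpoint that will be tested. Two things in its construction can move the result without any change in skin disease.

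The first is the denominator. Taken literally, it includes patients with a baseline of 0, who can never respond. It also includes patients with no baseline CLASI, since the pre-treatment exclusion in Section 7.1.1 is worded "If a patient is missing data during the pre-treatment period for SLEDAI-2K, PGA, or BILAG" and does not name CLASI. A programmer who follows Section 5.4 instead would drop the zero baselines. The percentage-change table of Section 7.2.8.2 and the response table of Section 7.2.8.1 could then describe different patients on the same score. There is a further trap. If zero baselines drop out only because their percentage is undefined, those who are medication failures or early withdrawals could still be kept as non-responders by rule.

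The second is the multiplier in CLASI-B. A factor of two that depends on a recalled answer is as large as the response threshold itself. Because 50% is written without a sign, it is also open whether a fall of exactly 50% counts.

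**Working it through.** **Plan's own figure.** The SAP gives no power or expected rate for CLASI response, so there is none to reproduce. Its only sizing figure is for SRI-4 (Section 3.3): 96 evaluable patients, 2:1, 62% vs 33%, two-sided 10%, 80% power. A continuity-corrected calculation returns 32 + 64 = 96. Without the correction the total is 81, and power at 96 is 86%. These rates are borrowed below for illustration only.

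**Zero baselines kept as non-responders.** Let p be the response rate among patients with baseline above 0 and f the zero-baseline share, equal in both arms. Each observed rate is (1 − f)p and the difference is (1 − f)(p₁ − p₀). The ratio of the rates does not change. Assumed: p₁ = 50%, p₀ = 30%, f = 20% to 40%.

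- f = 20%: 40% vs 24%, difference 16 points
- f = 30%: 35% vs 21%, difference 14 points
- f = 40%: 30% vs 18%, difference 12 points

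**Power: keeping versus excluding.** Rates of 62% vs 33% among patients with baseline above 0, 96 patients in all, two-sided 10%, power = Φ[(Δ − 1.645·SE₀)/SE₁], with SE₀ pooled, SE₁ unpooled and no continuity correction:

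| f | Difference if kept | Power if kept | n if excluded | Power if excluded (29 points) |
|---|---|---|---|---|
| 0% | 29.0 | 86% | 96 | 86% |
| 20% | 23.2 | 71% | 77 | 79% |
| 40% | 17.4 | 54% | 58 | 67.5% |

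In this illustration, exclusion gives more power than keeping the zeros, despite the smaller n.

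**CLASI-B with unchanged skin.** Let D be the undoubled dyspigmentation sum (13 sites scored 0 or 1, so at most 13) and S the scarring plus scalp score. A change of answer from at least 12 months to less than 12 months takes the total from 2D + S to D + S, a fall of D/(2D + S).

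- S = 0: D/2D = 50.0% for every D from 1 to 13 (for example 8 to 4, or 26 to 13)
- D = 13, S = 1: 13/27 = 48.1%, the largest fall possible at S = 1
- D = 4, S = 1: 4/9 = 44.4%
- D = 4, S = 3: 4/11 = 36.4%
- D = 1, S = 1: 1/3 = 33.3%

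The opposite change of answer raises the score by D/(D + S), which is 100% when S = 0. The answer alone therefore makes a responder only when S = 0 and the threshold includes 50%. The smaller artificial shifts still enter the damage-score ANCOVA of Section 7.2.8.2, which needs neither condition.

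**CLASI-A.** Its total is the left side of the form, and the duration item is not part of it. The effect is zero.

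**The SAP's own practice.** Sections 7.2.4.1 and 7.2.4.2 limit the steroid-reduction denominators to patients on oral steroids at baseline, and Section 7.2.4.3 limits its analysis to those at or above 7.5 mg/day. CLASI response has no equivalent condition.

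**The case against.** A reader could argue that 50% improvement is a percentage change, so the zero-baseline exclusion in Section 5.4 already applies by default. That reading is possible. However, Section 7.2.8.1 sets its own denominator and does not refer to that rule, and Section 5.4 gives way where another section states otherwise. The text leaves the matter open, and its literal sense keeps these patients.

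The size is uncertain, and that objection stands. No document gives the zero-baseline share. The baseline split of CLASI activity at 8 says nothing about zeros. The SLEDAI-2K and BILAG worksheets call for CLASI when skin items are present, so some patients without skin disease may have no CLASI and already fall outside the denominator. With blinded, randomised groups, zeros kept as non-responders should mainly weaken the difference and should not favour one arm.

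Parts of Sections 4.2 and 7.2.8.1 are redacted. A repeat in patients with higher baseline activity may be there and cannot be called missing.

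A reader might go further and infer that neither rate measures skin response. The SAP does not support this. CLASI-A is at most diluted, and CLASI-B is open to misclassification only when S = 0 and the threshold is inclusive. Counting a 0-to-0 patient as a responder is also a strained reading, since no change is not an improvement.

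One might also say that 210 days is too short to observe a 12-month duration. The item asks what usually happens, by patient report, so it records history and does not depend on follow-up in the trial. What stands is that nothing holds the answer constant.

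**Conclusion.** The point holds as a defect of definition in a tested secondary endpoint. The stated denominator for CLASI response has no baseline condition, is not reconciled with Section 5.4, and the threshold has no inequality sign. If zero-baseline patients are kept as non-responders, the difference shrinks by (1 − f): from 20 points to between 16 and 12 for f of 20% to 40%. Both the share and the 50% vs 30% rates are assumptions, and f is taken as equal in the two arms.

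For CLASI-B, a changed duration answer with unchanged skin produces a fall of exactly 50% when there is no scarring or scalp score and a smaller one otherwise. How often answers change is unknown, so no rate of false response can be stated. CLASI-A is not exposed to this, and the SRI-4 primary analysis is unaffected by either issue.

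**What to change.** In Section 7.2.8.1:

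- Define response as a reduction of ≥ 50% from baseline.
- Restrict the CLASI-A denominator to FAS patients with baseline total activity above 0, and the CLASI-B denominator to those with baseline total damage above 0.
- Apply the same restriction to medication failures and early withdrawals, so that a zero-baseline patient cannot re-enter as a non-responder by rule.
- Refer to the zero-baseline rule in Section 5.4, so that response and percentage change cover the same patients.

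Add a CLASI-B sensitivity analysis, for response and for the damage-score ANCOVA, that holds each patient's duration answer at its baseline value. The main score can stay as printed on the form. Replacing it with an undoubled sum, or dropping the CLASI-B test, would be a preference and is not needed to correct the fault.

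The cost is SAP wording, a re-run of existing tables and one added sensitivity table. No new data are needed. The downside is smaller denominators.

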#### 7.2.8.2. Results, Changes, and Percentage Change from Baseline in CLASI

The analysis of CLASI total activity score and CLASI total damage score will be performed separately using an ANCOVA model with change or percentage change from baseline to each nominal visit as the dependent variable, treatment group as the factor, and the corresponding baseline CLASI score as a covariate. The p-value for the difference between the BOS161721 and placebo groups at each nominal visit is based on the F-test.

Descriptive statistics for the activity score and damage score will be summarized separately at baseline and each visit. Change and percentage change from baseline will be summarized at each post-baseline visit. The LS Mean estimate, its standard error and 90% CI will be tabulated

by treatment group and for the difference between treatment groups (BOS161721 versus placebo) for change and percentage change at each visit. Statistical methods described in Section 7.1.1 will be implemented. In case of missing data, LOCF methods will be implemented as described in Section 5.4 and Section 7.2.1 for the “at each visit” analyses. Individual components of the CLASI will not be carried forward; however, the total activity score or total damage score may be carried forward from the most recent prior visit. If the most recent prior visit is missing, occurred more than 30 days before (current visit date – most recent prior visit date  $> 30$ ), or is not evaluable, LOCF is not implemented. The analyses will be performed in line with the two approaches outlined in Section 7.2.6.2. **CCI**

Statistical testing data will be omitted from MAD Phase 1b treatment group displays.

CLASI observed results will be presented in data listings for all randomized patients.

#### 7.2.9. Results, Changes, and Percentage Changes from Baseline in Swollen, Tender, and Active Joints ACR-28

The ACR-28 joint count evaluates the number of tender and swollen joints in the shoulder, elbow, wrist, hand, knee joints. Joints of the feet, hip and ankle are excluded. The sum of active joints is also evaluated and is defined as the total number of joints with swelling and tenderness in the same joint. The joint sums for tender and swollen joints are recorded in the database. The sum of active joints will be derived.

The analysis of ACR-28 Swollen and Tender Joints for the sum of tenderness (left and right), the sum of swelling (left and right), and sum of active joints (left and right) will be performed separately using an ANCOVA model with change and percentage change from baseline to each nominal visit as the dependent variable, treatment group as the factor, and the baseline ACR-28 score as a covariate. The p-value for the difference between the BOS161721 and placebo groups at each nominal visit is based on the F-test.

Descriptive statistics for the tenderness, swelling, and derived active joint sums will be summarized separately at baseline and each visit. Change and percentage change from baseline will be summarized at each post-baseline visit. The LS Mean estimate, its standard error and 90% CI will be tabulated by treatment group and for the difference between treatment groups (BOS161721 versus placebo) for change and percentage change at each visit.

Statistical methods described in Section 7.1.1 will be implemented. In case of missing data, LOCF methods will be implemented as described in Section 5.4 and in Section 7.2.1 for the “at each visit” analyses. Individual components of ACR-28 will not be carried forward; however, the total ACR-28 score may be carried forward from the most recent prior visit. If the most recent prior visit is missing, occurred more than 30 days before (current visit date – most recent prior visit date  $> 30$ ), or is not evaluable, LOCF is not implemented. The analyses will be performed in line with the two approaches outlined in Section 7.2.6.1.

Sponsor: Boston Pharmaceuticals, Inc.  
Protocol Number: BOS161721-02  
SAP Version and Date: Version 4.0, 23Apr2021

The mean and SD of the change from baseline in ACR-28 sum of tenderness, sum of swelling, and sum of active joints based on primary analysis methods will be presented graphically over time by study phase and treatment group.

Statistical testing data will be omitted from MAD Phase 1b treatment group displays.

Swollen, tender, and active joints ACR-28 observed results will be presented in data listings for all randomized patients.

#### 7.2.10. Systemic Lupus Erythematosus Disease Activity Index 2000 (SLEDAI-2K)

The SLEDAI-2K is a validated instrument that measures disease activity in SLE patients at the time of the visit and in the previous 30 days. It is a global index and includes 24 clinical and laboratory variables that are weighted by the type of manifestation, but not by severity. The total score falls between 0 and 105, with higher scores representing increased disease activity. The SLEDAI-2K has been shown to be a valid and reliable disease activity measure in multiple patient groups. A SLEDAI 2K of 6 or more generally represents moderately to severely active disease.

##### 7.2.10.1. Proportion of Patients with a SLEDAI-2K Response

The proportion of patients with a SLEDAI-2K response, defined as  $\geq$  4-point reduction from baseline in SLEDAI-2K total score, will be summarized by study phase and treatment group in the FAS overall and by nominal visit. Statistical methods described in Section 7.1.1 will be implemented. In case of missing data, LOCF methods will be implemented as described in section 5.4 and Table 1 and in Section 7.2.1 for the “at each visit” analyses.

The analyses described in Section 7.1.1 and Table 2 (Primary Analysis methods and Sensitivity Analysis 2 methods) will be repeated for each nominal visit as described in Section 7.2.1 based on the SLEDAI-2K response definition and will be presented by study phase and treatment group in the FAS.

The denominators for analyses will be the number of patients in the FAS with an evaluable post-baseline SLEDAI-2K assessment (overall analysis) or with evaluable SLEDAI-2K assessment (whether observed or imputed via LOCF depending on the analysis) at a given visit (nominal visit analysis).

Statistical testing data will be omitted from MAD Phase 1b treatment group displays.

##### 7.2.10.2. Results, Changes, and Percentage Change from Baseline in SLEDAI-2K

The analysis of SLEDAI-2K will be performed using an ANCOVA model with change and percent change from baseline to each nominal visit as the dependent variable, treatment group as the factor, and the baseline SLEDAI-2K score as a covariate. The SLEDAI-2K total score is

Sponsor: Boston Pharmaceuticals, Inc.  
Protocol Number: BOS161721-02  
SAP Version and Date: Version 4.0, 23Apr2021

calculated and provided in the clinical database. In case of missing data, SLEDAI-2K will be recalculated outside the clinical database after application of imputation rules.

Descriptive statistics for the SLEDAI-2K total score will be summarized separately at baseline and each visit. Change and percentage change from baseline will be summarized at each post-baseline visit. The LS mean estimate, its standard error and 90% CI will be tabulated by treatment group and for the difference between treatment groups (BOS161721 versus placebo) for change and percentage change at each visit. The p-value for the difference between the BOS161721 and placebo groups at each nominal visit is based on the F-test.

Statistical methods described in Section 7.1.1 will be implemented,. In case of missing data, LOCF methods will be implemented as described in section 5.4 and Table 1 and in Section 7.2.1 for the “at each visit” analyses. The analyses will be performed in line with the two approaches outlined in Section 7.2.6.1.

Approach 1 corresponding to the primary analysis methods (LOCF for missing data, medication failure LOCF) will be repeated for subgroups CCI [REDACTED] as defined below:

